[REDACTED]

[REDACTED]

Clinical Laboratory

[REDACTED]

Biostatistics and Data Management

[REDACTED]

SYNOPSIS

Sponsor: Aerie Pharmaceuticals, Inc.
Name of Finished Product: Netarsudil 0.02% and 0.04% Ophthalmic Solution
Name of Active Ingredients: Netarsudil
Study Title: A prospective, double-masked, randomized, multicenter, placebo-controlled, parallel-group study assessing the safety and ocular hypotensive efficacy and optimum concentration to be used clinically of netarsudil ophthalmic solution in Japanese/Japanese-American subjects with open-angle glaucoma or ocular hypertension in the United States
Study Number: AR-13324-CS205
Study Phase: 2
Primary Objective(s): In this Phase 2 study, the primary objectives are to evaluate: 
• The ocular hypotensive efficacy of netarsudil ophthalmic solution relative to its placebo over a 28-day period• The ocular and systemic safety of netarsudil ophthalmic solution relative to its placebo over a 28-day period
Secondary Objective(s): None.
Study Design: This will be a 28-day, double-masked, randomized, multicenter, placebo-controlled, parallel group efficacy and safety trial evaluating reduction of elevated intraocular pressure (IOP) with netarsudil ophthalmic solution. The purpose of this study is to assess the efficacy and safety of netarsudil ophthalmic solution (0.02% and 0.04%) compared to its placebo in Japanese or Japanese-American subjects that are at least 18 years of age with open-angle glaucoma (OAG) or ocular hypertension (OHT). All investigational products will be dosed in both eyes (OU) once daily (QD) in the evening (PM). Subjects eligible to be enrolled in this study will be those of Japanese ethnicity within the second generation, with a diagnosis of either OAG or OHT that are on treatment with a topical ocular hypotensive medication. Approximately 180 subjects will be enrolled in this study. Subjects who agree to participate in this study and are enrolled will attend a total of 6 study visits: a Screening Visit, Qualification Visit #1, Qualification Visit #2/Day 1 (baseline), Week 1 (Day 8), Week 2 (Day 15), and Week 4 (Day 29). Subjects currently using ocular hypotensive medications will be required to washout of their pre-study ocular hypotensive medication for a prescribed period (i.e., 5 days to at least 4 weeks, depending on the medication) prior to attending Qualification Visit #1. Subjects eligible to be enrolled in this study must meet all inclusion criteria and none of the exclusion criteria at each of the Screening Visit and Qualification Visits #1 and #2. Subjects will receive a baseline eye examination including IOP measurements at the Screening Visit and Qualification Visits #1 and #2 and, if deemed eligible, will be enrolled at Qualification Visit #2 and assigned to placebo or 1 of 2 investigational products in a 1:1:1 ratio according to a computer-generated randomization list. Randomization will take place using IWRS methodology and will stratify subjects by site. Randomized subjects will dose the assigned investigational product in both eyes QD in the evening (between 20:00 and 22:00 hours) beginning on Day 1 and up to and including the evening prior to the final visit at

Visit 6 (Week 4). Procedures conducted at each of study Visits 4-6 will include safety measures and efficacy measurements, including IOP assessments. At Visits 4-6 (Weeks 1, 2, and 4, respectively), IOP will be assessed at 08:00, 10:00 and 16:00 hours. Following completion of the Visit 6 (Week 4) study visit procedures, subjects will exit the study. For subjects who discontinue early, every possible effort will be made to assure there is a final visit that includes all examinations listed for Visit 6.0 (Week 4) and dilated ophthalmoscopy.

Inclusion Criteria:

Subjects have to meet all of the following criteria at screening and qualification visits to enter into the study:

1. Must be 18 years of age or older
2. Be of Japanese ethnicity within the second generation proven by birth certificate or family tree. Japanese generation is defined as follows: 1st generation is defined as born in Japan, immigrated to US; 2nd generation is defined as parents are 1st generation, however, the subject was born in US as an American citizen
3. Diagnosis of open-angle glaucoma (OAG) or ocular hypertension (OHT) in both eyes (OAG in one eye and OHT in the fellow eye is acceptable)
4. Medicated intraocular pressure (IOP) \geq 15 mmHg and $<$ 30 mmHg in both eyes at screening visit (this also applies to treatment naïve subjects)
5. For OAG eyes, unmedicated (post washout) IOP \geq 15 mmHg and $<$ 35 mmHg in the study eye at 2 qualification visits (08:00 hour), 2-7 days apart. At second qualification visit IOP \geq 15 mmHg and $<$ 35 mmHg at 10:00 and 16:00 hours (in the same eye).
6. For OHT eyes, unmedicated (post washout) IOP \geq 22 mmHg and $<$ 35 mmHg in the study eye at 2 qualification visits (08:00 hour), 2-7 days apart. At second qualification visit IOP \geq 22 mmHg and $<$ 35 mmHg at 10:00 and 16:00 hours (in the same eye).
7. Best corrected visual acuity + 1.0 logMAR or better by ETDRS in each eye (equivalent to 20/200 or better Snellen visual acuity in each eye)
8. Be able and willing to give signed informed consent and follow study instructions

Exclusion Criteria:

Subjects meeting any of the following criteria during screening or qualification evaluations (e.g., at the time of randomization) will be excluded from entry into the study:

Ophthalmic:

1. Clinically significant ocular disease (e.g., corneal edema, uveitis, or severe keratoconjunctivitis sicca) which might interfere with interpretation of the study efficacy endpoints or with safety assessments, including subjects with glaucomatous damage so severe that washout of ocular hypotensive medications for up to 8 weeks is not judged safe as it would put the subject at risk for further vision loss
2. Pseudoexfoliation or pigment dispersion component glaucoma, history of angle closure glaucoma, or narrow angles (i.e., Shaffer Grade 2 or less). Note: Previous laser peripheral iridotomy is NOT acceptable
3. Intraocular pressure \geq 35 mmHg (unmedicated) in either eye (individuals who are excluded for this criterion are not allowed to attempt requalification)
4. Ocular hyperemia score of moderate (+ 2) at Qualification Visit #2
5. Previous glaucoma intraocular surgery, including selective laser trabeculoplasty (SLT) or argon laser trabeculoplasty (ALT) in either eye
6. Refractive surgery in either eye (e.g., radial keratotomy, photorefractive keratectomy [PRK], laser-assisted in situ keratomileusis [LASIK], corneal cross-linking)
7. Ocular trauma within the 6 months prior to screening, or ocular surgery or non-refractive laser treatment within the 3 months prior to screening
8. Recent or current evidence of ocular infection or inflammation in either eye. Current evidence of clinically


significant blepharitis, conjunctivitis, keratitis, or a history of herpes simplex or zoster keratitis in either eye at screening
 
9. Use of ocular medication in either eye of any kind within 30 days of screening and throughout the study, with the exception of a) ocular hypotensive medications (which must be washed out according to the provided schedule), b) lid scrubs (which may be used prior to, but not after, screening), c) lubricating drops for dry eye (which may be used throughout the study), or d) non-steroid allergy drops (note: must not contain a vasoconstrictor) as prescribed by the Investigator
 
10. Mean central corneal thickness using optical pachymetry greater than 620 μm in either eye at screening
 
11. Any abnormality preventing reliable applanation tonometry of either eye (e.g., keratoconus)
 
12. Known hypersensitivity to benzalkonium chloride or excipients of netarsudil ophthalmic solution
 
Systemic:
 
13. Clinically significant abnormalities in laboratory tests at screening
 
14. Clinically significant systemic disease which might interfere with the study
 
15. Participation in any investigational study within 30 days prior to screening
 
16. Systemic medication that could have a substantial effect on IOP within 30 days prior to screening, or anticipated during the study, including any corticosteroid-containing drug regardless of route of administration
 
17. Women of childbearing potential who are pregnant, nursing, planning a pregnancy, or not using a medically acceptable form of birth control. An adult woman is considered to be of childbearing potential unless she is 1 year post-menopausal or 3 months post-surgical sterilization. All females of childbearing potential must have a negative urine pregnancy test result at the screening examination and must not intend to become pregnant during the study

Study Population:
 
A total of approximately 180 Japanese/Japanese-American subjects will be enrolled in this study at approximately 35 investigational sites in the US comprising a total of 60 subjects per treatment arm for each of the 3 treatment arms. Subjects will be at least 18 years of age with diagnosed OAG or OHT, each of whom meets all inclusion criteria and none of the exclusion criteria.


Investigational Product, Dose, and Mode of Administration:
 
• Netarsudil Ophthalmic Solution 0.02%, 1 drop QD (PM), OU• Netarsudil Ophthalmic Solution 0.04%, 1 drop QD (PM), OU• Netarsudil Ophthalmic Solution Placebo, 1 drop QD (PM), OU

Duration of Treatment:
 
Dosing will continue daily for 28 days continuously.

Efficacy Assessments:
 
The primary efficacy outcome will be the comparison of netarsudil ophthalmic solutions (0.02% and 0.04%) relative to placebo for mean diurnal IOP within a treatment at Week 4 (Day 29) by Goldmann Applanation Tonometry.
 
Secondary efficacy outcomes will be comparison of netarsudil ophthalmic solutions relative to placebo for:
 
• Mean diurnal IOP at Weeks 1 and 2 (Days 8 and 15, respectively)• Mean change from baseline in mean diurnal IOP at each post-treatment visit• Mean percent change from baseline in mean diurnal IOP at each post-treatment visit• Mean IOP at each post-treatment time point• Mean change from diurnally adjusted baseline IOP at each post-treatment time point

- Mean percent change from diurnally adjusted baseline IOP at each post-treatment time point
- Percentages of subjects achieving pre-specified mean, mean change, and percent mean change in mean diurnal IOP levels

Other secondary efficacy analyses may be carried out as described in the study Statistical Analysis Plan.

Safety Assessments:

The primary safety measures in both eyes of enrolled subjects will include:

- Ocular symptoms/adverse events
- Best corrected visual acuity
- Objective findings of biomicroscopic examinations (i.e., anterior segment examinations including evaluation of cornea, conjunctiva, lids, and lens)
- Dilated ophthalmoscopy, including vertical cup-disc ratio measurements

Other safety assessments will be:

- Systemic safety assessments as measured by heart rate, blood pressure, and clinical laboratory evaluations (including hematology, clinical chemistry, and urinalysis)
- Pregnancy testing (for women of child bearing potential)

Statistical Methods:

The primary efficacy endpoint is the mean diurnal IOP across subjects within treatment group at Week 4. Assuming a two-sided test with $\alpha = 0.05$ and a common standard deviation (SD) of 3.5 mmHg at each time point yielding a common SD of 3.0 for the diurnal mean assuming a correlation among time points of 0.60, 49 ITT subjects per arm yields at least 90% power to demonstrate superiority of netarsudil (0.02% or 0.04%) to placebo in mean diurnal study eye IOP (average of 08:00, 10:00, and 16:00 hours) at the Week 4 Visit assuming a difference of at least 2.0 mmHg in the mean diurnal IOP. The study will be considered a success and superiority of netarsudil to placebo will be concluded if the two-sided p-value ≤ 0.05 at Week 4. With 60 ITT subjects per arm, each test has 95% power to demonstrate superiority of netarsudil (0.02% or 0.04%) to placebo.

The primary analysis of the primary outcome will employ a linear model with mean diurnal IOP at Week 4 as the response, baseline mean diurnal IOP as a covariate, and treatment as a main effect factor, using the intent to treat population with Monte Carlo Markov Chain multiple imputation techniques used to impute missing data. The least squares mean differences (netarsudil – placebo) will be presented separately for netarsudil 0.02% and 0.04% as well as 2-sided p-values and 95% confidence intervals (CIs). Inference will be made on the 2-sided p-values. Superiority for a concentration (0.02% and 0.04%) will be concluded if the 2-sided p-value, for testing the difference (netarsudil – placebo) to 0, ≤ 0.05 and the point estimate of the difference < 0 at Week 4 for that concentration.

There will be no adjustment for the multiplicity of the 2 active concentrations (0.02% and 0.04%) tested against placebo in this Phase 2 study.

Date of Original Approved Protocol (Rev 0): 17 July 2017

Date of Most Recent Protocol Amendment (if applicable): Not applicable.

Prepared in: Microsoft Word 2016

TABLE OF CONTENTS

SYNOPSIS	4
LIST OF ABBREVIATIONS AND DEFINITIONS OF TERMS	12
1. INTRODUCTION	14
1.1 Investigational Product	14
1.2 Findings from Non-clinical and Clinical Studies	15
1.3 Risks and Benefits to Human Subjects	15
2. STUDY OBJECTIVES	16
2.1 Primary Objective(s)	16
2.2 Secondary Objective(s).....	16
3. INVESTIGATIONAL PLAN	17
3.1 Overall Study Design and Plan.....	17
3.2 Rationale for Study Design and Control Group	18
3.3 Expected Duration of Subject Participation.....	18
4. STUDY POPULATION SELECTION	19

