2. STUDY OBJECTIVES

2.1 Primary Objective(s)

In this Phase 2 study, the primary objectives are to evaluate:

[figure not shown]
- The ocular hypotensive efficacy of netarsudil ophthalmic solution relative to its placebo over a 28-day period
- The ocular and systemic safety of netarsudil ophthalmic solution relative to its placebo over a 28-day period

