3.1 Overall Study Design and Plan

This will be a 28-day, double-masked, randomized, multicenter, placebo-controlled, parallel-group efficacy and safety trial evaluating reduction of elevated IOP with netarsudil ophthalmic solution. The purpose of this study is to assess the efficacy and safety of netarsudil ophthalmic solution (0.02% and 0.04%) compared to its placebo in Japanese or Japanese-American subjects that are at least 18 years of age with OAG or OHT.

All investigational products will be dosed in both eyes (OU) QD in the evening (PM). Subjects eligible to be enrolled in this study will be those of Japanese ethnicity within the second generation, with a diagnosis of either OAG or OHT that are on treatment with a topical ocular hypotensive medication. Approximately 180 subjects will be enrolled. Subjects who agree to participate in this study and are enrolled in the study will attend a total of 6 study visits: a Screening Visit, Qualification Visit #1, Qualification Visit #2/Day 1 (baseline), Week 1 (Day 8), Week 2 (Day 15), and Week 4 (Day 29).

Subjects currently using ocular hypotensive medications will be required to washout of their pre-study ocular hypotensive medication for a prescribed period (i.e., 5 days to at least 4 weeks, depending on the medication) prior to attending Qualification Visit #1. Subjects

eligible to be enrolled in this study must meet all inclusion criteria and none of the exclusion criteria at each of the Screening Visit and Qualification Visits #1 and #2. Subjects will receive a baseline eye examination including IOP measurements at the Screening Visit and Qualification Visits #1 and #2 and, if deemed eligible, will be enrolled at Qualification Visit #2 and assigned to placebo or 1 of 2 investigational products in a 1:1:1 ratio according to a computer-generated randomization list. Randomization will take place using Interactive Web Response System (IWRS) methodology and will stratify subjects by site.

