8.2 Efficacy Variables and Primary Hypotheses

1. The primary efficacy outcome will be the comparison of each netarsudil group to placebo for:
 - Mean diurnal IOP within a treatment group at the Week 4 study visit (Day 29) by Goldmann Applanation Tonometry.
2. Secondary efficacy endpoints will include the comparison of each netarsudil group to placebo for:
 - Mean diurnal IOP at Weeks 1 and 2 (Days 8 and 15, respectively)
 - Mean change from baseline in mean diurnal IOP at each post-treatment visit
 - Mean percent change from baseline in mean diurnal IOP at each post-treatment visit
 - Mean IOP at each post-treatment time point
 - Mean change from diurnally adjusted baseline IOP at each post-treatment time point

- Mean percent change from diurnally adjusted baseline IOP at each post-treatment time point
 - Percentages of subjects achieving pre-specified mean, mean change, and percent mean change diurnal IOP levels at each post-treatment time point:
 - Diurnal mean IOP of ≤ 22 , ≤ 21 , ≤ 20 , ≤ 19 , ≤ 18 , ≤ 17 , ≤ 16 , ≤ 15 , ≤ 14
 - IOP reduction from baseline of ≥ 4 , ≥ 6 , ≥ 8 , ≥ 10 , ≥ 12 (IOP reduction at a visit from baseline was calculated as $\text{IOP} [\text{baseline}] - \text{IOP} [\text{visit}]$, using mean [integral or non-integral] IOP values)
 - IOP percent reduction from baseline of ≥ 5 , ≥ 10 , ≥ 15 , ≥ 20 , ≥ 25 , ≥ 30 , ≥ 35 , ≥ 40 (IOP percent reduction at a visit from baseline was calculated as $[\text{IOP reduction from baseline} / \text{IOP (baseline)}] * 100\%$)
3. The primary hypotheses are:
- H_{01} : The difference between study eyes treated with netarsudil 0.02% and study eyes treated with placebo (netarsudil 0.02% - placebo), in mean diurnal IOP at Week 4 is equal to 0.
 - H_{11} : The difference between study eyes treated with netarsudil 0.02% and study eyes treated with placebo (netarsudil 0.02% - placebo), in mean diurnal IOP at Week 4 is not equal to 0.
 - H_{02} : The difference between study eyes treated with netarsudil 0.04% and study eyes treated with placebo (netarsudil 0.04% - placebo), in mean diurnal IOP at Week 4 is equal to 0.
 - H_{12} : The difference between study eyes treated with netarsudil 0.04% and study eyes treated with placebo (netarsudil 0.04% - placebo), in mean diurnal IOP at Week 4 is not equal to 0.

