8.3 Analysis Methods

All continuous study assessments will be summarized by treatment and time point (as applicable) using descriptive statistics (n, mean, median, SD, minimum, and maximum). All categorical study assessments will be summarized by treatment and time point (as applicable) using frequency counts and percentages. All statistical tests will be performed at a 2-sided 5%

significance level. For the IOP measurements, 2-sided tests and 2-sided 95% confidence intervals will be reported.

Mean diurnal IOP values will be constructed by averaging the three IOP measurements on each of Week 1, Week 2, and Week 4. Mean diurnal baseline IOP will be constructed as the average of the three Day 1 IOP measurements. Mean change from mean baseline diurnal IOP will be created by taking the average of the three-time points on each of Week 1, Week 2, and Week 4 and subtracting the mean baseline diurnal IOP measurement.

For diurnally adjusted IOP measures, baseline will refer to the time-relevant measure at Visits 3.0 through 3.2 (e.g., IOP at 08:00 hours at Visit 3.0 will be the baseline for 08:00 hours at Visits 4.0, 5.0, and 6.0; IOP at 10:00 hours at Visit 3.1 will be the baseline for 10:00 hours at Visits 4.1, 5.1, and 6.1). For mean diurnal IOP, baseline will refer to the mean diurnal IOP at Visit 3. For all other variables, baseline is defined as the last measurement prior to the first dose of study medication. Change from baseline will be calculated as follow-up visit – baseline visit.

Percent change from diurnally adjusted baseline IOP will be determined by dividing the change from diurnally adjusted baseline by the corresponding baseline IOP value, such that a negative change from baseline will produce a negative percent change from baseline.

An abbreviated list of primary and secondary efficacy variables, along with the planned analysis methods for those variables, are given in Table 8-1. Note that each subject will have one eye designated as the study eye. Only study eyes will be evaluated for all the efficacy measures; however, both eyes will be treated. Fellow eyes will be evaluated separately for the primary analysis of the primary efficacy measure.

Table 8-1 Summary of Efficacy Variables and Analysis Methods

	Two Sample T-test ^a	ANCOVA ^b	MMRM ^c	Fisher's Exact Test ^d	Analysis Population	Data Used for Analysis
Primary Analysis						
Mean diurnal IOP at Week 4		X			ITT	Observed data
Secondary Analyses						

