8.3.1 Primary Efficacy Analyses

Only observed data will be used for efficacy analyses. The primary analysis of the primary outcome will employ a linear model with mean diurnal IOP at Week 4 as the response, baseline mean diurnal IOP as a covariate, and treatment as a main effect, using the ITT population. The treatment differences (netarsudil – placebo) between each netarsudil group and placebo will be

tested. The least squares mean differences (netarsudil – placebo) will be presented separately for netarsudil 0.02% and 0.04% as well as 2-sided p-values and 95% confidence intervals (CIs). However, no statistical inference will be made.

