8.3.2 Secondary Efficacy Analyses

The secondary efficacy analyses will include additional analyses of the primary efficacy endpoint as well as other analyses of the secondary endpoints, as outlined below.

The primary efficacy analysis will be repeated on the PP population.

Secondary analyses of the primary endpoint will be completed using individual two-sample t-tests and 95% t-distribution confidence intervals for each comparison (each netarsudil group vs placebo) using the ITT and PP populations.

Similar analyses will be completed on the secondary endpoints based on the ITT and PP populations: mean change from baseline in mean diurnal IOP at each post-treatment visit, mean IOP at each post-baseline time point, and mean change from diurnally adjusted baseline IOP at each post-treatment time point. Models adjusting for baseline will only be performed on the mean IOP response variable as inference is identical between this response and the change from baseline IOP response variable in such a model based on the PP and ITT populations.

Additionally, for the mean IOP values at each post-treatment time visit, mixed model repeated measures will be run with mean IOP baseline as the covariate; treatment, visit, time point, treatment by visit, treatment by time point, and treatment by visit by time point as the fixed effects; and subject as the repeated measure. An unstructured covariance structure will be used model covariances. This model will be run including the Week 1, Week 2, and Week 4 visits based on the ITT population only.

Graph will also be provided for mean IOP values by treatment group, visit, and time point.

Percent change from baseline in mean diurnal IOP at each post-treatment visit and percentage change from diurnally adjusted baseline IOP at each post-treatment time point will be analyzed using two-sample t-tests, between each netarsudil group and placebo, at each time point and visit, including two-sample t-tests and 95% t-distribution confidence intervals on the difference (netarsudil – placebo). The analysis will be based on ITT population only.

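### Does the title's optimum-concentration aim require a planned 0.04% versus 0.02% comparison, and does the pairwise Fisher wording in the SAP matter?

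*Protocol*

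**What the plan says.** The title states that the study is "assessing the safety and ocular hypotensive efficacy and optimum concentration to be used clinically of netarsudil ophthalmic solution". The aim is not carried further. The efficacy objective in Protocol 2.1 is "The ocular hypotensive efficacy of netarsudil ophthalmic solution relative to its placebo over a 28-day period", Protocol 2.2 lists no secondary objective, and Protocol 3.1 says "The purpose of this study is to assess the efficacy and safety of netarsudil ophthalmic solution (0.02% and 0.04%) compared to its placebo".

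The SAP follows the same line. Section 8.2 gives one hypothesis pair for each concentration, both against placebo, and introduces its secondary list with "Secondary efficacy endpoints will include the comparison of each netarsudil group to placebo for". In section 8.3.1 the least squares mean differences from the primary model "will be presented separately for netarsudil 0.02% and 0.04% as well as 2-sided p-values and 95% confidence intervals", each defined as netarsudil minus placebo. The t-tests in 8.3.2 have the same direction. The repeated-measures model in 8.3.2 takes "treatment, visit, time point, treatment by visit, treatment by time point, and treatment by visit by time point as the fixed effects", so it includes all three arms, but it names no contrasts. Section 8.3 adds that "All continuous study assessments will be summarized by treatment and time point (as applicable) using descriptive statistics".

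For the responder levels, the closing paragraph of SAP 8.3.2 applies Fisher's exact test pairwise among the treatment groups at each visit. Protocol 9.6.2 and Table 8-1 footnote d name the same test for each netarsudil group against placebo only. SAP 8.2 restricts the endpoint comparison to placebo without naming a test, and describes the endpoint as "Percentages of subjects achieving pre-specified mean, mean change, and percent mean change diurnal IOP levels at each post-treatment time point".

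**The concern.** A title that promises to assess the best concentration suggests that the two concentrations will be compared. A reader who looks for that comparison finds no objective, hypothesis, sample-size statement or selection rule for it, and no sentence saying that an adjusted 0.04% minus 0.02% difference will be tabulated. If none were shown, the trial would be silent on a question in its own title, and a reader could set two placebo differences side by side without any measure of how poorly they are separated.

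The Fisher wording adds to this. Taken literally, SAP 8.3.2 makes the responder analysis the only described efficacy comparison between concentrations, as p-values on dichotomised pressure, while two other passages rule that comparison out. The passages also differ over visit and time point. Two programmers could produce different tables.

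**Working it through.** **Inputs.** Protocol 9.2 and SAP 2.6 give an SD of 3.5 mmHg per time point, a correlation of 0.60 among three time points, two-sided α of 0.05, a 2.0 mmHg difference from placebo, 49 per arm for at least 90% power, and 95% power at 60 per arm. SAP 8.2 expects about 10 ITT subjects per arm. The baseline-outcome correlation r and the true difference between concentrations are not given, so both appear below as assumed ranges.

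**The plan's own figures.**
- SD of the diurnal mean = 3.5 × √((1 + 2 × 0.60)/3) = 2.997, stated as 3.0.
- For 2.0 mmHg and SD 3.0, the noncentral t gives 49 per arm for 90% power (0.904 at 49) and 0.952 at 60. The stated figures reproduce.

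**Is the adjusted dose estimate missing?** SAP 8.3.1 fits one linear model with all three arms and baseline. Write d1 for 0.02% minus placebo and d2 for 0.04% minus placebo. Then 0.04% minus 0.02% = d2 − d1, because the placebo term cancels. For precision, take n per arm, residual variance σ² and balanced baselines: Var(d1) = Var(d2) = 2σ²/n and Cov(d1, d2) = σ²/n, so Var(d2 − d1) = 2σ²/n + 2σ²/n − 2σ²/n = 2σ²/n. With equal arms the printed placebo intervals therefore show approximately the half-width that applies to the dose difference. In addition, the sample code in Protocol Appendix 7 requests least squares mean differences with no control level, which outputs all three pairs with intervals. The SAP drops the imputation that this code served, so it is not a commitment, but the same request on observed data would print the row.

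**What would the row show?** Half-width = t(0.975, 3n − 4) × 3.0 × √(1 − r²) × √(2/n).

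| n per arm | r = 0 | r = 0.3 | r = 0.5 | r = 0.7 |
|---|---|---|---|---|
| 10 (df 26) | 2.76 | 2.63 | 2.39 | 1.97 |
| 60 (df 176) | 1.08 | 1.03 | 0.94 | 0.77 |

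- The half-width at 10 per arm falls to 2.0 mmHg only when r reaches √(1 − (2.0/2.758)²) = 0.69.
- The unadjusted interval from the arm summaries, on 18 df, is ±2.82.
- With uneven arms of 8, 10 and 12 (placebo, 0.02%, 0.04%) and r = 0, the placebo contrasts are ±2.93 and ±2.81 and the dose contrast ±2.64.
- Power for an assumed 1.0 mmHg difference between concentrations is 44% at 60 per arm and about 10% at 10 per arm. Even the full design was sized for the placebo comparisons only.

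**The Fisher list.** SAP 8.2 gives 9 levels of attained pressure, 5 of reduction and 8 of percent reduction: 22 levels. Over three visits that is 22 × 3 = 66 tests per pair of arms, so 66 × 2 = 132 for the placebo comparisons or 66 × 3 = 198 for all pairs. The count is per visit because SAP 8.3 defines the diurnal mean as the average of the three readings on a visit day, so there is one value per visit. SAP 8.3.2 and Protocol 9.6.2 both name Weeks 1, 2 and 4. The references to time point in SAP 8.2 and footnote d are loose wording and do not create further tests.

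**The case for a change.** The strongest argument for acting is that the cost is nearly nil: one contrast from a model already fitted, one sentence of caution, one corrected phrase. With equal arms the dose contrast is about as precise as the placebo contrasts that the SAP still prints with p-values and intervals, so imprecision alone does not justify leaving it out. The SAP's statement on inadequate power refers to the primary hypotheses, which are the placebo hypotheses, and nowhere mentions the concentration question. Section 13 announces a reduced set of analyses and no added comparison, so the pairwise Fisher wording looks unintended.

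Much of this stands. The text does not commit to the row, the caveat does not name the title's question, and SAP 8.3.2 is out of line with Protocol 9.6.2 and footnote d. What does not follow is that the plan is deficient. Two concentrations can be judged through each one's effect against a common placebo together with safety, which is also a primary objective in Protocol 2.1. The safety sections of the SAP compare treatment groups for adverse events and hyperemia. Protocol 3.2 gives the reason for the study as checking that earlier results hold in Japanese subjects, and Protocol 1.2 says the concentrations were chosen from an earlier dose-ranging study. The table shells listed in SAP 16 are not available here and may already contain the row. SAP 1 and 11 allow further analyses if the study report identifies them.

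**Conclusion.** No change follows. The title is broader than the objectives, but the analyses match the objectives, hypotheses and sample size. The baseline-adjusted 0.04% minus 0.02% point estimate can be recovered exactly from the two differences that SAP 8.3.1 presents. Its interval, about ±2.76 mmHg at 10 per arm with SD 3.0 and no covariate gain (±1.97 if r were 0.7), would not separate the concentrations unless they differed by more than the interval's width allows. A reader already told that the analyses are informational and support no inference has no ground for treating the concentration question as settled.

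The pairwise Fisher phrase is a drafting slip. An analyst would sensibly follow Table 8-1 footnote d and Protocol 9.6.2 and run 132 tests per visit-based list. Running 198 instead would add descriptive p-values and alter no conclusion. This assessment rests on the SAP's expected 10 subjects per arm and its no-inference statement. If the trial had run to 60 per arm and been used to choose a concentration, the missing contrast would deserve more weight.
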